## List of abbreviations

|              |  |
|--------------|--|
| AE           | Adverse Event  |
| ALP          | Alkaline phosphatase                                       |
| ALT          | Alanine aminotransferase                                   |
| ANCOVA       | Analysis of Covariance                                     |
| AST          | Aspartate aminotransferase                                 |
| ATC          | Anatomical Therapeutic Chemical                            |
| BMI          | Body Mass Index  |
| BSA          | Body Surface Area  |
| CDLQI        | Children's Dermatology Life Quality Index                  |
| CHAQ         | Childhood Health Assessment Questionnaire                  |
| CHMP         | Committee for Medicinal Products for Human Use             |
| COVID        | Coronavirus Disease  |
| CRF          | Case Report/Record Form (paper or electronic)              |
| CSR          | Clinical Study Report                                      |
| CTCAE        | Common Terminology for Adverse Events                      |
| DMC          | Data Monitoring Board                                      |
| ECG          | Electrocardiogram  |
| FAS          | Full Analysis Set  |
| FDA          | United States Food and Drug Administration                 |
| GGT          | Gamma-glutamyl transferase                                 |
| HA           | Health Authorities   |
| IGA mod 2011 | Novartis Investigator's Global Assessment modified in 2011 |
| IRT          | Interactive Response Technology                            |
| LOCF         | Last Observation Carried Forward                           |
| MACE         | Major Adverse Cardiovascular Events                        |
| MAP          | Master Analysis Plan                                       |
| MAR          | Missing at Random  |
| MedDRA       | Medical Dictionary for Regulatory Activities               |

---

|            |  |
|------------|--|
| MI         | Multiple Imputation                    |
| MMRM       | Mixed- effects Repeated Measures Model |
| [REDACTED] | [REDACTED]                             |
| NMQ        | Novartis MedDRA Query                  |
| NovDTD     | Novartis Drug and Therapy Dictionary   |
| PASI       | Psoriasis Area and Severity Index      |
| PEA        | Primary Endpoint Analysis              |
| PD         | Protocol Deviation                     |
| [REDACTED] | [REDACTED]                             |
| [REDACTED] | [REDACTED]                             |
| PT         | Preferred Term                         |
| QTcF       | Fridericia QT Correction               |
| SAE        | Serious Adverse Event                  |
| s.c.       | Subcutaneous                           |
| SD         | Standard Deviation                     |
| SOC        | System Organ Class                     |
| [REDACTED] | [REDACTED]                             |
| TBL        | Total Bilirubin                        |
| VAS        | Visual Analogue Scale                  |
| WBC        | White blood cells                      |

## 1 Introduction

Data will be analyzed by [REDACTED] according to the data analysis section 9 of the protocol, which is available in [Appendix 16.1.1 of the CSR](#). Important information is given in the following sections and details are provided, as applicable, in [Appendix 16.1.9 of the CSR](#).

This document contains the detailed statistical and analytical plans for full analysis of CAIN457A2310 study and covers aspects for Week 24 primary endpoint analysis (PEA) and Week 52 full analysis, with reference to the study protocol amendment 3.

SAPs were finalized and approved with version controls:

[figure not shown]
- A2310 SAP 1.0 (dated 14-April-2017): first version of the analysis plan
- A2310 SAP amendment 1.0 (dated 06-May-2019): amendment to the SAP after dry run prior to the Week 24 database lock
- A2310 SAP addendum (dated 07-Sep-2019): addendum to the SAP post Week 24 database lock
- A2310 SAP amendment 2.0 (dated 23-Oct-2019): amendment to the SAP after dry run prior to the Week 52 database lock (current version)
- A2310 SAP amendment 3.0 (dated 18-Dec-2020): amendment to the SAP prior to the Week 104 database lock (current version)

### 1.1 Study design

This is a multicenter, randomized, double-blind, placebo-and active-controlled (etanercept in single blinded arm) study in pediatric subjects aged 6 years to less than 18 years with severe chronic plaque psoriasis. Approximately 160 subjects aged 6 years to <18 years will be enrolled, of which at least 30 pediatric subjects will be 6 years to <12 years old. In reality around 40-45 patients will be needed to meet the requirement of recruiting about 30% of subjects in the < 25kg weight group.

Subjects will be randomized using a 1:1:1:1 ratio into one of the treatment arms: secukinumab low dose, secukinumab high dose, etanercept or placebo. The randomization will be stratified by age (<12 years or ≥12 years) and weight (<25 kg, 25-<50 kg, ≥50kg) at randomization. Subjects randomized to the placebo group will be pre-assigned to either the low- or high-dose group of secukinumab, at the Randomization visit, in case they are not achieving a PASI 75 response as assessed at Week 12.

The study consists of 5 Epochs: screening (up to 4 weeks), induction (of 12 weeks), maintenance (of 40 weeks), extension treatment epoch (open-label of 184 weeks) and post-treatment follow-up epoch (of 16 weeks). The detailed information of the study design is described in [Figure 1-1](#).

**Figure 1-1** Study design

The following study periods will be considered for analysis:

- **Screening period** (before Randomization)
- **Induction period** (Randomization to Week 12 pre-dose), including follow-up period (F4, F8, F12 and F16 (EOF) visits) for prematurely discontinued subjects before Week 12 completion. For placebo PASI 75 responders at Week 12, subjects will enter follow-up period after Week 12, including the first visit F4 and four weeks later visit EOF at F8.
- **Maintenance period** (Week 12 dose to Week 52 pre-dose), including follow-up period (F4, F8, F12 and F16 visits) for prematurely discontinued subjects before Week 52 completion, and for etanercept patients with the completion of the maintenance epoch.
- **Extension period** (Week 52 dose until Week 236 (EOT)), including follow-up period (F4, F8, F12 and F16 visits) for prematurely discontinued subjects before Week 236 completion.
- **Entire treatment period** (Randomization to Week 236 (EOT)), for safety analysis, exposure including follow-up period up to last dose + 84 days.
- **Entire study period** (Randomization to end of study (EOS)), including follow-up period (F4, F8, F12 and F16 visits).

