### **3      Investigational plan**

#### **3.1      Study design**

[figure not shown]
This is a multicenter, randomized, double-blind, placebo- and active-controlled (etanercept in single blinded arm) study in pediatric subjects aged 6 years to less than 18 years with severe chronic plaque psoriasis. Approximately 160 subjects aged 6 years to <18 years will be enrolled, of which at least 30 will be 6 years to <12 years old. It is expected that subjects will be enrolled at approximately 70 study sites worldwide.

Two age subgroups will be studied in a staggered approach within this clinical study: 12 to less than 18 years of age, and 6 to less than 12 years of age (age for the subgroups determined at the time of randomization). Enrolment of children aged 6 to less than 12 years will begin after a favorable recommendation by an independent external Data Monitoring Committee (DMC) who will review data of approximately 80 (approximately 40 treated with secukinumab) enrolled adolescents (aged 12 to less than 18 years) treated for 28 weeks. Adolescents will continue to be recruited while the data from the first 80 subjects are being collected and analyzed.

Subjects will be randomized using a 1:1:1:1 ratio into one of the treatment arms: secukinumab low dose, secukinumab high dose, etanercept or placebo. Subjects randomized to secukinumab treatment arms (high dose and low dose) will receive dose based on the weight category (<25 kg, 25 to <50kg,  $\geq$ 50 kg). If a subject moves into a higher or lower weight group at two consecutive visits with weight measurements during the maintenance (from Week 12 onwards as assessed at monthly visits, i.e. Week 13, 14, 15 will not be taken into account) or during extension treatment period (as assessed at scheduled site visits), the subject will receive dosing according to the new (higher or lower) weight group respectively.

**Figure 3-1** Study design

The study consists of 5 Epochs: screening (up to 4 weeks), induction (of 12 weeks), maintenance (of 40 weeks), extension treatment epoch (open-label of 184 weeks) and post-treatment follow-up epoch (of 16 weeks). An outline of the visits is presented in [Figure 3-1](#), while a detailed visit and assessment schedule can be found in [Table 6-1](#), [Table 6-2](#).

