#### **Stratification**

Randomization will be stratified by age and body weight collected at Randomization Visit. This stratification ensures balanced allocation of subjects to treatment groups within the age and weight strata.

The age strata is “age < 12” or “age  $\geq$  12”. The weight strata will be “body weight < 25 kg”, “25 kg  $\leq$  body weight < 50 kg” or “body weight  $\geq$  50 kg”. Stratification by age and body weight will occur at Randomization Visit. For the randomization at Randomization Visit, it will be targeted to have at least approximately 30% of the subjects in each weight stratum.

The randomization scheme for subjects will be reviewed and approved by a member of the IQS Randomization Group.

Within each weight stratum, subjects will be assigned to the high dose or the low dose treatment group for secukinumab or placebo (see [Table 5-1](#)).

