## **9.7      Sample size calculation**

Approximately 160 pediatric subjects from 6 to less than 18 years of age, with 2 subgroups: 6 to less than 12 years of age, and 12 to less than 18 years of age.

Stratification is planned for age (<12 years,  $\geq$ 12 years) and weight (<25kg, 25-<50kg and  $\geq$ 50kg). It will be targeted to have at least 30 subjects in the <12 years subgroup at a minimum. Enrollment of children aged 6 to less than 12 years will proceed after efficacy and

safety data for approximately 80 (approximately 40 treated with AIN) enrolled adolescents (aged 12 to less than 18 years) treated for 28 weeks have been reviewed and deemed satisfactory by a Data Monitoring Committee.

Since two secukinumab dose regimens will be tested versus placebo with respect to the co-primary endpoints (PASI 75 response and IGA 0 or 1 response at Week 12), the type-I-error will be split to 1.25% one-sided for each comparison. With 40 subjects per group and assuming a response rate of 10% for PASI 75 response and IGA 0 or 1 response in the placebo group, the power to show a response rate of 65% for PASI 75 response and 45% for IGA 0 response in the secukinumab groups based on Fisher's exact test (nQuery Advisor 7.0, two group Fisher's-exact test of equal proportions) is approximately 99% for PASI 75 response and approximately 88% for IGA mod 2011 0 or 1 response. For the secondary endpoint of PASI 90 response at week 12, assuming a response rate of 8% in the placebo group, the power to show a significant difference between a secukinumab dose and placebo, assuming a response rate of 39% in the secukinumab groups based on Fisher's exact test (nQuery Advisor 7.0, two group Fisher's-exact test of equal proportions) is approximately 82% for PASI 90 response. The assumed response rates for secukinumab are based on the confirmatory efficacy in severe patients in the adult phase III program. At Week 12, PASI 75 response rates of 11% and PASI 90 response rates of 7% have been reported in the placebo group in [Paller et al \(2008\)](#) for children and adolescents aged 4-17 years.

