**Table 2-6 Subgroup analyses**

| Endpoint/analysis                   | Randomization strata including age and weight | Previous psoriasis therapy* |
|-------------------------------------|---|-----------------------------|
| PASI 75/90 response @ Week 12       | X   | X                           |
| IGA mod 2011 0/1 response @ Week 12 | X   | X                           |
| Adverse event                       | X   |                             |

Note: presented are only those endpoints that need subgroup analyses.

\*: only for “Previous < systemic > therapy” and embedded subgroup “failure”.

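### Below 25 kg both secukinumab arms receive 75 mg, yet the planned Week 12 weight-stratum analyses compare each arm with placebo separately and list no pooled comparison with placebo

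*SAP*

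**What the plan says.** **Dose.** Protocol 3.3, 5.2 and Table 5-1 assign 75 mg to both secukinumab arms below 25 kg, given as one 0.5 mL injection. Reassignment to a new weight category starts only from Week 12 (Protocol 3.1). The two arms therefore have the same planned treatment up to the Week 12 assessment.

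**Subgroup analysis.** SAP Table 2-6 plans PASI 75/90 and IGA 0/1 at Week 12, and adverse events, by "Randomization strata including age and weight". SAP 5.1.2.2 gives the model for the weight subgroups. It is the same exact logistic regression with the weight-stratum term dropped, and it yields odds ratios for the secukinumab dose regimens against control.

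**Pooled group.** SAP 4.1 forms a group of subjects under 25 kg on 75 mg. It does so among additional analyses performed after the Week 24 database lock, with non-responder imputation. Its list of groups contains no placebo group.

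**Stratum size.** Protocol 5.3 says "it will be targeted to have at least approximately 30% of the subjects in each weight stratum". Protocol 3.1 plans about 160 subjects, "of which at least 30 will be 6 years to <12 years old", and Protocol 9.7 adds: "It will be targeted to have at least 30 subjects in the <12 years subgroup at a minimum". SAP 1.1 repeats the minimum and continues: "In reality around 40-45 patients will be needed to meet the requirement of recruiting about 30% of subjects in the < 25kg weight group". On allocation, SAP 1.1 says: "Subjects will be randomized using a 1:1:1:1 ratio into one of the treatment arms: secukinumab low dose, secukinumab high dose, etanercept or placebo".

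**The concern.** Below 25 kg, low dose and high dose are two labels for one regimen. A subgroup table that reports them separately gives two estimates of the same effect, each from half of the treated children. Any difference between the two columns is chance, but a reader could take it for a dose response. This is also the stratum where the trial has fewest children to spare, and the only one that informs 75 mg in children of this weight.

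The number expected in the stratum is also unclear. The protocol's 30% target and the SAP's 40-45 do not agree, and the SAP does not say whether 40-45 counts children under 12 or patients under 25 kg.

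**Working it through.** **1. The plan's own power.** Inputs (Protocol 9.7, SAP 3): 40 per arm, 1.25% one-sided, Fisher's exact test. Power is the sum of Bin(x; n1, p1) × Bin(y; n0, p0) over all outcomes (x, y) whose one-sided Fisher p-value is at most 0.0125.

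| Endpoint | Rates | Recomputed | Printed |
|---|---|---|---|
| PASI 75 | 65% vs 10% | 99.9% | about 99% |
| IGA 0/1 | 45% vs 10% | 88.4% | about 88% |
| PASI 90 | 39% vs 8% | 82.1% | about 82% |

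The printed figures reproduce, so the method matches the plan's.

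**2. Stratum size.** 0.30 × 160 = 48, or 48/4 = 12 per arm. The SAP's figures give 40/160 = 25.0% and 45/160 = 28.1%, or 10 to about 11 per arm. The shortfall is 3 to 8 patients. Conversely, 40-45 is 30% of 40/0.30 = 133 to 45/0.30 = 150 subjects. The age minimum alone is 30/160 = 18.8%.

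If 40-45 counts children under 12, the stratum is smaller by however many of them weigh 25 kg or more. The documents give no weight distribution by age. As an assumption, if 50% to 70% of 45 such children weigh under 25 kg, the stratum is 22.5 to 31.5 patients (14.1% to 19.7% of 160).

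**3. Power in the stratum, by arm and pooled.** The formula and threshold are those of step 1. The pooled comparison has 2n on 75 mg and n on placebo.

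| Per arm (stratum total) | PASI 75: one arm | PASI 75: pooled | IGA 0/1: one arm | IGA 0/1: pooled | PASI 90: one arm | PASI 90: pooled |
|---|---|---|---|---|---|---|
| 12 (48) | 57% | 81% | 19% | 31% | 14% | 21% |
| 10 (40) | 52% | 69% | 14% | 26% | 9% | 18% |
| 6 (24, assumed) | 20% | 33% | 4% | 6% | 2% | 3% |

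**4. Precision, PASI 75 difference.** The 95% half-width is 1.96 × √(0.65×0.35/n1 + 0.10×0.90/n0).

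- 12 per arm: one arm, 1.96 × √(0.01896 + 0.00750) = 32 points; pooled, 1.96 × √(0.00948 + 0.00750) = 26 points.
- 10 per arm: one arm, 1.96 × √(0.02275 + 0.00900) = 35 points; pooled, 1.96 × √(0.01138 + 0.00900) = 28 points.

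**The case against.** **By-arm tables respect the randomization.** Under the intent-to-treat principle in SAP 2.2, subjects are analysed in the arm assigned. This stands, and it is a reason to keep the by-arm columns. It is no reason to leave out a pooled one: the two arms were each randomized against placebo within the stratum, so their union is too.

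**The SAP already pools.** SAP 4.1 has the 75 mg group under 25 kg. That is true, but as listed it is a set of response rates without a placebo comparator, added after the Week 24 lock.

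**The subgroups are outside the controlled testing strategy.** This also stands. Using 1.25% here is a yardstick carried over from the sample size section, not a test the plan makes in the stratum. The half-widths in step 4 show the same gain without it.

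**Stronger readings of the size mismatch.** A reader might infer that the 30% target cannot be reached. The documents do not support this. The 30 children under 12 are a floor, 40-45 is an estimate of need, and nothing caps enrolment under 12. Up to 160 − 80 = 80 places could remain after the adolescents whose data are reviewed, and 48/80 = 60%. The 80 is itself a maximum, because adolescents continue to be recruited meanwhile. With words such as around and about, 28% is arguably close to 30%.

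A reader might also infer that the <25 kg result is far weaker than the plan implies. No power or precision is stated for any subgroup. Going from 48 to 40 patients lowers one-arm PASI 75 power only from 57% to 52%. Larger losses need an assumed weight distribution.

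**Conclusion.** The point holds as a weakness in how the <25 kg subgroup is reported. Splitting one regimen into two columns gives up available information. Pooling adds 24 percentage points of PASI 75 power at 12 per arm and 17 at 10 per arm, and narrows the confidence interval by 6 to 7 points on each side.

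The size rests on the plan's assumed rates applying in this stratum, on equal allocation within it, and on unadjusted Fisher tests standing in for the exact logistic model. Pooling does not enlarge the placebo group. For IGA 0/1 and PASI 90 power stays at 31% or less even when pooled, so the stratum remains descriptive.

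The mismatch between 40-45 and 48 is real but minor: 3 to 8 patients, and more only if the figure counts children under 12 of whom some weigh 25 kg or more. It does not touch the primary analysis, which uses all subjects, and it gives no ground for lowering the Protocol 5.3 target. Rewriting that target as a share the age minimum would deliver would turn a floor into a ceiling.

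**What to change.** 1. In the weight-stratum tables for PASI 75, PASI 90 and IGA 0/1 at Week 12 (SAP 2.3 and 5.1.2.2), add for the <25 kg stratum a comparison of pooled 75 mg (low plus high arm) with placebo. Use the same model and missing-data methods as the other columns. Keep the by-arm columns, with a footnote that both arms received the same dose.
2. Label the <25 kg results descriptive.
3. In SAP 1.1, reconcile 40-45 with the Protocol 5.3 target (48 of 160), state whether it counts children under 12 or patients under 25 kg, and report the actual <25 kg number per arm. The current SAP amendment is dated 18-Dec-2020, after the last Week 52 visit of 18 September 2019, so that number is known and no recruitment decision is involved. Leave the Protocol 5.3 target as it is.

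The cost is one extra column, a footnote and one corrected sentence. No new patients or data are needed, and the alpha-controlled tests do not change. Because the pooled comparison is added after the locks, it should be listed in SAP 4.1 as an added analysis.

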
## 1.2 Study objectives and endpoints

The primary objective of the study is to demonstrate the superiority of secukinumab (low and high dose) in pediatric subjects with severe chronic plaque psoriasis with respect to both PASI

75 and IGA mod 2011 0 or 1 response (co-primary endpoints) at Week 12, compared to placebo.

Following are the secondary objectives:

- To demonstrate superiority of secukinumab (low and high dose) in subjects with severe chronic plaque psoriasis with respect to PASI 90 response at Week 12, compared to placebo.
- To assess efficacy of secukinumab in subjects with severe chronic plaques psoriasis with respect to PASI 50 and PASI 100 at Week 12, compared to placebo.
- To assess efficacy of secukinumab in subjects with severe chronic plaque psoriasis with respect to PASI 50, PASI 75, PASI 90, PASI 100 and IGA mod 2011 0 or 1 at Week 16 and over time up to Week 52 (will consider up to week 24, for Week 24 PEA).
- To assess the efficacy of secukinumab with respect to changes in PASI score and IGA mod 2011 score at Week 12, compared to placebo, and over time up to Week 52 (will consider up to week 24, for Week 24 PEA).
- To investigate the effects of treatment with secukinumab with respect to changes in CDLQI at Week 12, compared to placebo, and over time up to Week 52 (will consider up to week 24, for Week 24 PEA).
- To investigate the effects of treatment of secukinumab with respect to CDLQI 0 or 1 achievement at Week 12, compared to placebo, and over time up to Week 52 (will consider up to week 24, for Week 24 PEA).
- To evaluate the effects of treatment of secukinumab on disability at Week 12 and over time up to Week 52 (will consider up to week 24, for Week 24 PEA) by use of CHAQ®, for subjects with history of psoriatic arthritis.
- To investigate the clinical safety and tolerability of secukinumab as assessed by growth, weight gain, tolerability of s.c. injections, vital signs, clinical laboratory variables, ECGs, and adverse events monitoring, compared to placebo.

**Table 1-1 Primary, secondary [REDACTED] efficacy variables**

| Variable   | Type          |
|--|---------------|
| PASI 75 at Week 12, compared to Placebo  | Co-primary    |
| IGA mod 2011 0 or 1 response at Week 12, compared to Placebo   | Co-primary    |
| PASI 90 response at Week 12, compared to Placebo   | Key secondary |
| PASI 50, PASI 75, PASI 90, PASI 100, IGA mod 2011 0 or 1 compared to Placebo over time up to Week 52 (or Week 24, for PEA) | Secondary     |
| Change from baseline in PASI score over time up to Week 52 (or Week 24, for PEA)   | Secondary     |
| IGA mod 2011 score over time up to Week 52 (or Week 24, for PEA)   | Secondary     |
| Change in CDLQI over time up to Week 52 (or Week 24, for PEA)  | Secondary     |
| CDLQI 0 or 1 achievement over time up to Week 52 (or Week 24, for PEA)   | Secondary     |
| Change in CHAQ over time up to Week 52 (or Week 24, for PEA)   | Secondary     |

## 2 Statistical methods

## 2.1 Data analysis general information

This document covers the statistical analysis plan for Week 24 PEA analysis, Week 52 analysis and final analysis.

█████ will perform the analyses at week 24 and week 52 and final analysis. Statistical software SAS version 9.4 or later will be used.

Summary statistics for continuous variables will be presented with n, mean, standard deviation, minimum, lower quartile (Q1), median, upper quartile (Q3) and maximum for observed values and change from baseline. Summary statistics for discrete variables will be presented in contingency tables and will include absolute and relative frequencies.

P-values will be presented as one-sided for hypothesis testing and as two-sided for other analysis. Two-sided 95% confidence intervals will be displayed. If not otherwise specified, hypothesis testing will be based on one-sided p-values that the treatment effect is in favor of secukinumab. The level of significance will be set to 2.5% (one-sided, family-wise type-I-error). The 95% confidence intervals will not be used for decision making; they will only be used for estimation and will therefore always be two-sided.

All listings will be presented by treatment sequence.

Footnotes will generally be provided for

- abbreviations used in the output; abbreviations used on several outputs, e.g. for listings can be presented on a separate page and do not have to be repeated as footnotes on each listing
- sort order of categories, e.g. for sorting within MedDRA (Medical Dictionary for Regulatory Activities) hierarchy levels
- MedDRA version used for reporting of MedDRA coded data

Footnotes will generally NOT be given for

- units displayed on the output
- interpretation of results (e.g. “odds ratio larger than 1 favors active treatment”)
- information that can be retrieved from the statistical section of the CSR unless it is not identifiable from the output, e.g. explanation of analysis model used unless results of more than one model are displayed on an output
- derivations of variables (e.g. body mass index (BMI) will not be explained in a footnote)
- information that will be provided in the clinical study protocol and/or methods section of the CSR (e.g. baseline definition if this is specified in the statistical section of the CSR)

